9.6 Interim Analysis

Interim analysis will be performed based on an optimal two-stage design for Phase II survival trials. Specifically, an exponential distribution with an exact variance estimate of the one-sample log-rank test (OSLT) will be used for the two-stage design (Wu, 2015). Using the R function Optimal.rKJ, this two-stage design assuming an exponential distribution will enroll 14 patients at the first stage. At the time of interim analysis, each patient is followed for an event (disease progression or death) or is censored. If the first stage test statistic $Z_1 < 0.088$, we stop the trial for futility. Otherwise the trial continues to the second stage until a total of 21 evaluable patients is enrolled on the study. The final analysis will be conducted when all patients have been enrolled.

If the second stage test statistic $Z < 1.632$, we don't reject the null hypothesis and conclude no efficacy of the treatment. If $Z \geq 1.632$, we conclude that the treatment is promising.

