6.5 Duration of Follow-Up

Safety:

Patients will be followed for safety of the Cabozantinib/Pembrolizumab combination therapy for 100-days after the last dose of Pembrolizumab (or the combination).

Patients removed from the study treatment for unacceptable adverse event(s) will be followed until resolution or stabilization of the adverse event.

Survival:

Patients will be followed for disease progression and survival status up to 1 year post-therapy initiation or until death, whichever occurs first.

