9.2 Sample Size/Accrual Rate

The historical median PFS for 2nd line metastatic pancreatic cancer will be assumed to be 2.0 months. We hypothesize an improvement in PFS to 4.0 months for this combination regimen.

A sample of 21 evaluable patients will provide 80% power to detect this hypothesized improvement in PFS with 80% power based on a one-sided log-rank test with 5% alpha and an

exponential distribution with an interim analysis plan (Section 9.6). Patient accrual is projected for 24 months with an estimated enrollment of 1 patient per month and 6 months of follow-up after the last patient is enrolled in the trial. Assuming a 5% unevaluable or drop-out rate, a sample of 23 patients will be enrolled in the Phase II trial.

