9.4 Analysis of Primary Endpoint

PFS will be estimated using the Kaplan-Meier curve and median PFS and confidence interval will be calculated. The one sample log-rank test will be employed to test improvement in PFS with the combination regimen. Exploratory analysis using the Cox regression model to assess PFS adjusted for a few key clinical parameters will be performed. An intent-to-treat analysis, wherein all patients who received study drug, will be the primary analysis of the PFS outcome.

Given that the timing of radiology scans is every Q8 weeks (+/- 1-2 weeks) or scans as clinically indicated, we will consider the analysis of PFS as interval censored data. The SAS ICLIFETEST will be used for nonparametric survival analysis of interval-censored data while SAS LIFEREG can deal with parametric survival model with both interval and right censored data. The R package for interval censored data (icenReg) which can do nonparametric, parametric and semiparametric Cox models will also be implemented.

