Tumor Assessment to determine PFS and ORR		Imaging/scans will be assessed per RECIST and iRECIST and the results (PR, CR, etc.) will be noted in the eCRF to support interim analysis (initial 14 patients) and the final analysis if the trial is not stopped early for futility.					
Survival Status		Interim analysis will be conducted after the first 14 patients are enrolled and will be followed for an event (disease progression, death).	Survival Status will be ascertained until death or until 1-year post-treatment initiation.				
Early Discontinuation		X, (note reason for early DC of treatment and/or reason for removal from study participation)					
	Screening	Cycle 1	Cycles 2 - 8	Cycles 9-17	Safety 100-Days after final dose	1-year post-treatment initiation	Off -Study

FOOTNOTES to Study Calendar:

* Completion of pembrolizumab Q3W monotherapy consists of 35 treatments (approximately 2 years). Discontinuation of treatment may be considered for participants who have attained a confirmed complete response (CR) and have been treated for at least 8 cycles (at least 24 weeks), receiving at least 2 cycles of the combination including 2 doses of pembrolizumab and at least 80% of the planned doses of cabozantinib beyond the date when the initial CR was declared.

** **Exosomal lipids correlative:** Blood samples for exosomal lipids are optional, and will be obtained via another protocol for biospecimen sample collection. Patients enrolled on this trial will have to sign a separate consent for participation in the correlative studies. 10cc blood in lavender-top tube EDTA will be collected at pre-treatment and then, once monthly for 6-months (i.e., at the clinic visit for Cycles 2 – 7).

*** **Patient-derived organoids correlative:** Tumor tissue will be obtained via another protocol for collection of biospecimen samples. Patients enrolled on this trial will have to sign a separate consent for tissue collection (i.e., in order to participate in the correlative studies).

1: Con meds at screening: Record meds only if given within 28 days of treatment.

2: Con Meds after screening visit: CON meds should be recorded up to 30 days after the last dose of trial intervention should be recorded. If participants experience an SAE or ECI, concomitant medications administered 30 days after the last dose of trial intervention are to be recorded.

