13.5 Data Management

Data management will be performed by cross-team members at MCC. These team members will include representatives from the Data Management Team, Biostatistics and Bioinformatics SRF, and the Quality Assurance Office. They will work closely with study staff to ensure timely and accurate data submission. A protocol specific Data Management Plan (DMP) will be authored by a senior data manager in collaboration with the biostatistician and Principal Investigator with each expected to review and approve the finalization of the DMP. In order to maintain best clinical practices in data management, the DMP may include, but not be limited to CRF/eCRF design, database build and design, database training, edit check/validation specifications, study database testing/release, data and paper workflow, report, metrics, query/discrepancy management, management of external (including lab) data, medical coding, SAE handling/reconciliation, data transfers and database lock. The protocol-specific DMP will additionally define the schedule at which data will be accessed by data management and study statistician to perform statistical programming for conduct of data quality, data control, data management, generation of interim reports and statistical analysis. Cross-team members will collaborate to establish procedures and timelines for quality control, audits, query resolution, annual reports, interim analysis and final data analysis.

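### Section 9.6 dates the final PFS test at completion of enrolment, while Section 9.2 plans 6 months of follow-up after the last patient

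*Combined protocol and SAP*

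**What the plan says.** Section 9.6 describes a two-stage one-sample log-rank design: 14 patients in stage 1, stop for futility if Z1 is below 0.088, otherwise continue to 21 evaluable patients. It then states "The final analysis will be conducted when all patients have been enrolled" and gives the final rule, under which the treatment is called promising if Z is at least 1.632.

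Section 9.2 sizes the trial on a historical median PFS of 2.0 months against a target of 4.0 months. It projects accrual of 1 patient per month over 24 months, followed by "6 months of follow-up after the last patient is enrolled in the trial".

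Other sections bear on timing without setting a final-analysis date:

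- Section 6.5: "Patients will be followed for disease progression and survival status up to 1 year post-therapy initiation or until death, whichever occurs first". This is a per-patient limit, not a data cutoff.
- Section 9.4 notes that "the timing of radiology scans is every Q8 weeks" (with a window of 1-2 weeks) and names the test.
- The Section 11 calendar covers only the interim: "Interim analysis will be conducted after the first 14 patients are enrolled and will be followed for an event".
- Section 13.5 leaves timing to procedures outside the protocol: "Cross-team members will collaborate to establish procedures and timelines for quality control, audits, query resolution, annual reports, interim analysis and final data analysis".
- Section 9.8 ties results posting to completed follow-up of the last patient, but that governs posting and not the analysis.

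**The concern.** The only sentence that dates the primary efficacy test ties it to the end of enrolment and does not mention follow-up. The sample-size section assumes a further 6 months. A team following 9.6 as written would apply the 1.632 cutoff when the last patients have almost no follow-up and some have not had a first scheduled scan. The test would rest on fewer events and have less power than at the date 9.2 implies.

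Two available dates are also undesirable in themselves. The trial is open-label and single-arm, and Section 4.2.1 gives the principal investigator and the statistician access to study data at all times. The cutoff for the go/no-go decision should therefore be fixed beforehand and not left open to choice.

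**Working it through.** **Inputs from the protocol.** Section 9.2: medians 2.0 and 4.0 months, exponential survival, 21 evaluable, 23 enrolled, 1 patient per month, 6 months of follow-up after last enrolment. Section 9.6: stage 1 of 14 patients, cutoffs 0.088 and 1.632. Sections 9.4 and 11: scans every 8 weeks, with a window of up to 2 weeks.

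**Assumptions.** Patients enter at months 0, 1, ..., n-1. The interim takes place at the 14th entry. The cut is either on the day of last entry (+0) or 6 months later (+6).

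**1. The plan's own figures.** Enrolment reproduces: 21/0.95 = 22.1, rounded up to 23. A search for the optimal two-stage total, using three variance forms, gives:

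- 19, 20 or 23 with each patient's follow-up capped at 6 months;
- 14, 17 or 20 uncapped with 6 months of added follow-up;
- 19, 22 or 24 uncapped with analysis at last enrolment.

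The stated 21 is thus of the right order but does not show which timing the design assumed. The stage 1 size and the two cutoffs were not reproduced, and the follow-up value given to the design function is not stated. No claim is made here about what the trial was sized on.

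**2. Patients before their first scan.** 8 weeks is 1.84 months and 10 weeks is 2.30 months. At last entry the shortest follow-up times are 0, 1, 2, 3, ... months. Two patients are below 8 weeks and three are below 10 weeks. At +6 there are none.

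**3. Expected events at a 4.0-month median.** A patient with follow-up f has an event with probability 1 - 2^(-f/4). With r = 2^(-1/4) = 0.8409, the sum of 2^(-f/4) over f = 0 to n-1 is (1 - r^n)/(1 - r).

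- n = 21, +0: (1 - 0.0263)/0.1591 = 6.12, so 21 - 6.12 = 14.88 events.
- n = 21, +6: 6.12 × 2^(-1.5) = 2.16, so 21 - 2.16 = 18.84 events.
- n = 23: 16.83 at +0 and 20.82 at +6, by the same formula.

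For n = 21 the shortfall is 3.96 events, or 3.96/18.84 = 21%. With follow-up capped at 6 months per patient the counts are 11.63 and 13.58.

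**4. Power of the stated rule.** For each patient x is the observed time, and λ0 = ln 2/2 = 0.3466 per month. O is the number of events, E = λ0 Σx, and Z = (E - O)/√V, with V = E or V = (O + E)/2. The trial continues if Z1 ≥ 0.088 and succeeds if Z ≥ 1.632. Results for n = 21, with 400,000 simulated trials per scenario:

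| Entry and variance | Follow-up cap | Power at +0 | Power at +6 | Loss (points) |
|---|---|---|---|---|
| Fixed monthly, V = E | none | 85.2% | 89.7% | 4.5 |
| Fixed monthly, V = E | 12 months | 84.8% | 89.3% | 4.5 |
| Fixed monthly, V = E | 6 months | 80.3% | 84.7% | 4.4 |
| Uniform random, V = E | none | 83.5% | 89.3% | 5.8 |
| Uniform random, V = E | 12 months | 83.2% | 88.7% | 5.5 |
| Uniform random, V = E | 6 months | 78.7% | 84.4% | 5.7 |
| Fixed monthly, V = (O+E)/2 | none | 87.7% | 91.3% | 3.6 |
| Fixed monthly, V = (O+E)/2 | 6 months | 84.0% | 87.5% | 3.5 |

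Simulated type I error was between 3.5% and 5.3%. The grouping of progression times at 8-week scans is not modelled.

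**The case against.** The strongest reply is that there is no real conflict. The sentence stands in the interim-analysis section, directly after the text on continuing to 21 patients, so it may only distinguish the full-cohort test from the 14-patient look. Enrolment would then be a precondition, with 9.2 supplying the follow-up. The calendar pairs enrolment with follow-up for the interim, and 9.8 links posting to completed follow-up; both fit that reading. Section 13.5 also gives the data-access schedule to a data management plan that is not part of these documents. This reading is plausible and may be the intent. It does not remove the problem, because 9.6 states a trigger and nothing in the protocol corrects it.

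The second reply is that the effect is small. That stands. Losses above 5 points appear only with random entry, and the (O+E)/2 variance gives about 3.5. A cut 2 months after last enrolment would reduce the loss to about 1.5 to 2 points (89.8% against 91.3%, and 87.8% against 89.8%). Patients without a scan are censored, which the test accommodates. Neither variance used here is shown to be the exact variance estimate that 9.6 names.

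The third reply is that the input to the design function should be known before +6 months is fixed. Confirming it is sensible, but the correction does not depend on it: +6 months is the protocol's own plan, and power was higher at that date in every variant, without inflating type I error.

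**Conclusion.** The concern holds. Section 9.6 attaches the primary test to completion of enrolment, Section 9.2 plans 6 further months of follow-up, and no section reconciles them. If 9.6 is followed literally, the cost is about 4 expected events out of 19 and 3.5 to 5.8 points of power. Power at last enrolment still lies at or about the stated 80% (lowest 78.7%), so this is a modest loss that should be corrected. It does not invalidate the design. The inconsistency rests on the text alone. Its size rests on exponential survival, accrual of 1 patient per month, an interim at the 14th entry and a cut on the very day of last enrolment.

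**What to change.** Replace the sentence in Section 9.6 with: *The final PFS analysis will be conducted 6 months after the last patient is enrolled, as planned in Section 9.2.* While making the change, the statistician should record which follow-up value was entered in the design function.

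The cost is one sentence. The PFS result comes 6 months later than under the literal 9.6 reading and no later than 9.2 already implies. Sections 6.5 and 11 already provide follow-up and imaging to 12 months, so no visits or scans are added. As a side remark, the 1-year CR/PR proportion (objective 1.2.3) can be reported once the last patient reaches 12 months, from that same follow-up.

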9.7 Reporting and Exclusions

9.7.1 Evaluation of Toxicity

All patients who received study drug will be evaluable for toxicity and included in the safety analysis from the time of their first treatment with Cabozantinib and Pembrolizumab combination treatment.

9.7.2 Evaluation of Response

An intent-to-treat analysis will be employed for assessment of clinical endpoints. All patients who met the eligibility criteria and received the study medication are included in the primary analysis. Thus, an incorrect treatment schedule or drug administration does not result in exclusion from the analysis of primary endpoint and the response rate.

9.8 Clinical Trial Registration with NIH

All clinical treatment trials have to be registered into clinicaltrials.gov before opening to accrual and trial results have to be published. The MCC-CRO Regulatory unit ([contact]) supports investigators in completing registration and renewal of their trials to NIH system in conjunction with a representative from UKHC. Results of this trial will be released on Clinicaltrials.gov within 12 months after follow-up is completed (of final patient accrued). If the trial is stopped early, data will be posted within six months of the study's termination.

10. ADVERSE EVENTS: LIST AND REPORTING REQUIREMENTS

The definitions of an AE or SAE, as well as the method of recording, evaluating, and assessing causality of AE and SAE and the procedures for completing and transmitting AE, SAE, and other reportable safety event reports are listed below.

Adverse events, SAEs, and other reportable safety events will be reported by the participant (or, when appropriate, by a caregiver, surrogate, or the participant's legally authorized representative).

The investigator and any designees are responsible for detecting, documenting, and reporting events that meet the definition of an AE or SAE as well as other reportable safety events. Investigators remain responsible for following up AEs, SAEs, and other reportable safety events for outcome.

The investigator, who is a qualified physician, will assess events that meet the definition of an AE or SAE as well as other reportable safety events with respect to seriousness, intensity/toxicity and causality.

10.1 Adverse Event Characteristics

- **CTCAE term (AE description) and grade:** The descriptions and grading scales found in the revised NCI Common Terminology Criteria for Adverse Events (CTCAE) version 5.0 will be utilized for AE reporting. (<http://ctep.cancer.gov/reporting/ctc.html>)
All appropriate treatment areas should have access to a copy of the CTCAE version 5.0. CTCAE version 5.0 can be downloaded from http://ctep.cancer.gov/protocolDevelopment/electronic_applications/ctc.htm
- **Attribution of the AE:**
 - Definite – The AE is *clearly related* to the study treatment.
 - Probable – The AE is *likely related* to the study treatment.
 - Possible – The AE *may be related* to the study treatment.
 - Unlikely – The AE is *doubtfully related* to the study treatment.
 - Unrelated – The AE is *clearly NOT related* to the study treatment.

Adverse Event (AE) definition

- An AE is any untoward medical occurrence in a clinical study participant, temporally associated with the use of study intervention, whether or not considered related to the study intervention.
- NOTE: An AE can therefore be any unfavorable and unintended sign (including an abnormal laboratory finding), symptom, or disease (new or exacerbated) temporally associated with the use of a study intervention.
- NOTE: For purposes of AE definition, study intervention (also referred to as Merck product) includes any pharmaceutical product, biological product, vaccine, diagnostic agent, or protocol specified procedure whether investigational or marketed (including placebo, active comparator product, or run-in intervention), manufactured by, licensed by, provided by, or distributed by Merck for human use in this study.

Events meeting the AE definition

- Any abnormal laboratory test results (hematology, clinical chemistry, or urinalysis) or other safety assessments (eg, ECG, radiological scans, vital signs measurements), including those that worsen from baseline, considered clinically significant in the medical and scientific judgment of the investigator.
- Exacerbation of a chronic or intermittent pre-existing condition including either an increase in frequency and/or intensity of the condition.
- New conditions detected or diagnosed after study intervention administration even though it may have been present before the start of the study.
- Signs, symptoms, or the clinical sequelae of a suspected drug-drug interaction.
- Signs, symptoms, or the clinical sequelae of a suspected overdose of either study intervention or a concomitant medication.
- For all reports of overdose (whether accidental or intentional) with an associated AE, the AE term should reflect the clinical symptoms or abnormal test result. An overdose without any associated clinical symptoms or abnormal laboratory results is reported using the terminology “accidental or intentional overdose without adverse effect.”

Events NOT meeting the AE definition

- Medical or surgical procedure (e.g., endoscopy, appendectomy): the condition that leads to the procedure is the AE.
- Situations in which an untoward medical occurrence did not occur (social and/or convenience admission to a hospital).
- Anticipated day-to-day fluctuations of pre-existing disease(s) or condition(s) present or detected at the start of the study that do not worsen.
- Surgery planned prior to informed consent to treat a pre-existing condition that has not worsened.

Definition of SAE

If an event is not an AE per definition above, then it cannot be an SAE even if serious conditions are met.

An SAE is defined as any untoward medical occurrence that, at any dose:

- a. Results in death
- b. Is life-threatening

The term “life-threatening” in the definition of “serious” refers to an event in which the participant was at risk of death at the time of the event. It does not refer to an event, which hypothetically might have caused death, if it were more severe.

- c. Requires inpatient hospitalization or prolongation of existing hospitalization

Hospitalization is defined as an inpatient admission, regardless of length of stay, even if the hospitalization is a precautionary measure for continued observation. (Note: Hospitalization for an elective procedure to treat a pre-existing condition that has not worsened is not an SAE. A pre-existing condition is a clinical condition that is diagnosed prior to the use of a Merck product and is documented in the participant’s medical history.)

- d. Results in persistent or significant disability/incapacity

The term disability means a substantial disruption of a person’s ability to conduct normal life functions.

This definition is not intended to include experiences of relatively minor medical significance such as uncomplicated headache, nausea, vomiting, diarrhea, influenza, and accidental trauma (eg, sprained ankle) that may interfere with or prevent everyday life functions but do not constitute a substantial disruption.

- e. Is a congenital anomaly/birth defect

In offspring of participant taking the product regardless of time to diagnosis.

- f. Other important medical events

Medical or scientific judgment should be exercised in deciding whether SAE reporting is appropriate in other situations such as important medical events that may not be immediately life-threatening or result in death or hospitalization but may jeopardize the participant or may require medical or surgical intervention to prevent 1 of the other outcomes listed in the above definition. These events should usually be considered serious.

Examples of such events include invasive or malignant cancers, intensive treatment in an emergency room or at home for allergic bronchospasm, blood dyscrasias or convulsions that do not result in hospitalization, or development of drug dependency or drug abuse.

Additional events that require reporting in the same manner as SAE

In addition to the above criteria, AEs meeting either of the below criteria, although not serious per ICH definition, are reportable to Merck in the same time frame as SAEs to meet certain local requirements. Therefore, these events are considered serious by Merck for collection purposes.

- Is a new cancer (that is not a condition of the study)
- Is associated with an overdose of pembrolizumab

AE and SAE recording

When an AE/SAE occurs, it is the responsibility of the investigator to review all documentation (e.g., hospital progress notes, laboratory, and diagnostics reports) related to the event.

The investigator will record all relevant AE/SAE information on the AE CRFs/worksheets at each examination.

There may be instances when copies of medical records for certain cases are requested by the Merck. In this case, all participant identifiers, with the exception of the participant number, will be blinded on the copies of the medical records before submission to the Merck.

The investigator will attempt to establish a diagnosis of the event based on signs, symptoms, and/or other clinical information. In such cases, the diagnosis (not the individual signs/symptoms) will be documented as the AE/SAE.

Assessment of intensity/toxicity

- An event is defined as “serious” when it meets at least 1 of the predefined outcomes as described in the definition of an SAE, not when it is rated as severe.
 1. The investigator will make an assessment of intensity for each AE and SAE (and other reportable safety event) according to the NCI Common Terminology for Adverse Events (CTCAE), version 5. Any AE that changes CTCAE grade over the course of a given episode will have each change of grade recorded on the AE CRFs/worksheets.
 - Grade 1: Mild; asymptomatic or mild symptoms; clinical or diagnostic observations only; intervention not indicated.
 - Grade 2: Moderate; minimal, local or noninvasive intervention indicated; limiting age-appropriate instrumental activities of daily living (ADL).
 - Grade 3: Severe or medically significant but not immediately life-threatening; hospitalization or prolongation of hospitalization indicated; disabling; limiting self-care ADL.
 - Grade 4: Life threatening consequences; urgent intervention indicated.
 - Grade 5: Death related to AE.

Assessment of causality

1. Did Merck product cause the AE?
2. The determination of the likelihood that Merck product caused the AE will be provided by an investigator who is a qualified physician. The investigator's signed/dated initials on the source document or worksheet that supports the causality noted on the AE form, ensures that a medically qualified assessment of causality was done. This initialed document must be retained for the required regulatory time frame. The criteria below are intended as reference guidelines to assist the investigator in assessing the likelihood of a relationship between the test product and the AE based upon the available information.
3. The following components are to be used to assess the relationship between Merck's product and the AE; the greater the correlation with the components and their respective elements (in number and/or intensity), the more likely Merck product caused the AE:

Exposure: Is there evidence that the participant was actually exposed to Merck product such as: reliable history, acceptable compliance assessment (pill count, diary, etc.), expected pharmacologic effect, or measurement of drug/metabolite in bodily specimen?

Time Course: Did the AE follow in a reasonable temporal sequence from administration of Merck product? Is the time of onset of the AE compatible with a drug-induced effect (applies to studies with investigational medicinal product)?

Likely Cause: Is the AE not reasonably explained by another etiology such as underlying disease, other drug(s)/vaccine(s), or other host or environmental factors.

Dechallenge: Was Merck product discontinued or dose/exposure/frequency reduced?

If yes, did the AE resolve or improve?

If yes, this is a positive dechallenge.

If no, this is a negative dechallenge.

(Note: This criterion is not applicable if: (1) the AE resulted in death or permanent disability; (2) the AE resolved/improved despite continuation of the Merck product; (3) the study is a single-dose drug study; or (4) Merck product(s) is/are only used 1 time.)

Rechallenge: Was the participant re-exposed to Merck product in this study?

If yes, did the AE recur or worsen?

If yes, this is a positive rechallenge.

If no, this is a negative rechallenge.

(Note: This criterion is not applicable if: (1) the initial AE resulted in death or permanent disability, or (2) the study is a single-dose drug study; or (3) Merck product(s) is/are used only 1 time.)

NOTE: IF A RECHALLENGE IS PLANNED FOR AN AE THAT WAS SERIOUS AND MAY HAVE BEEN CAUSED BY MERCK PRODUCT, OR IF RE-EXPOSURE TO MERCK'S PRODUCT POSES ADDITIONAL POTENTIAL SIGNIFICANT RISK TO THE PARTICIPANT THEN THE RECHALLENGE MUST BE APPROVED IN ADVANCE BY THE SPONSOR AS PER DOSE MODIFICATION GUIDELINES IN THE PROTOCOL, AND IF REQUIRED, THE INIRB/IEC.

4. Consistency with study intervention profile: Is the clinical/pathological presentation of the AE consistent with previous knowledge regarding Merck product or drug class pharmacology or toxicology?
5. The assessment of relationship will be reported on the case report forms/worksheets by an investigator who is a qualified physician according to his/her best clinical judgment, including consideration of the above elements.
6. Use the following scale of criteria as guidance (not all criteria must be present to be indicative of Merck product relationship).
 - Yes, there is a reasonable possibility of Merck product relationship:
 - There is evidence of exposure to the Merck product. The temporal sequence of the AE onset relative to the administration of Merck product is reasonable. The AE is more likely explained by Merck product than by another cause.
 - No, there is not a reasonable possibility of Merck product relationship:
 - Participant did not receive the Merck product OR temporal sequence of the AE onset relative to administration of the Merck product is not reasonable OR the AE is more likely explained by another cause than the Merck product. (Also entered for a participant with overdose without an associated AE.)
7. For each AE/SAE, the investigator must document in the medical notes that he/she has reviewed the AE/SAE and has provided an assessment of causality.
8. There may be situations in which an SAE has occurred and the investigator has minimal information to include in the initial report to the Merck. However, it is very important that the investigator always make an assessment of causality for every event before the initial transmission of the SAE data to Merck.
9. The investigator may change his/her opinion of causality in light of follow-up information and send an SAE follow-up report with the updated causality assessment.
10. The causality assessment is 1 of the criteria used when determining regulatory reporting requirements.
11. For studies in which multiple agents are administered as part of a combination regimen, the investigator may attribute each AE causality to the combination regimen or to a single agent of the combination. In general, causality attribution should be assigned to the combination regimen (ie, to all agents in the regimen). However, causality attribution may be assigned to a single agent if in the investigator's opinion, there is sufficient data to support full attribution of the AE to the single agent.

Follow-up of AE and SAE

- The investigator is obligated to perform or arrange for the conduct of supplemental measurements and/or evaluations as medically indicated to elucidate the nature and/or causality of the AE or SAE as fully as possible. This may include additional laboratory tests or investigations, histopathological examinations, or consultation with other health care professionals.
- New or updated information will be recorded in the CRF.

- The investigator will submit any updated SAE data to Merck within 2 business days but no longer than 3 calendar days of receipt of the information.

Reporting of AEs, SAEs, and Other Reportable Safety Events to the Merck SAE reports and any other relevant safety information are to be forwarded to the Merck Global Safety [contact]

A copy of all 15 Day Reports and Annual Progress Reports is submitted as required by FDA, European Union (EU), Pharmaceutical and Medical Devices agency (PMDA) or other local regulators. Investigators will cross reference this submission according to local regulations to the Merck Investigational Compound Number (IND, CSA, etc.) at the time of submission. Additionally, investigators will submit a copy of these reports to Merck & Co., Inc. (Attn: Worldwide Product Safety; [contact]) at the time of submission to FDA.

Adverse events (AEs), SAEs, and other reportable safety events will be reported by the participant (or, when appropriate, by a caregiver, surrogate, or the participant's legally authorized representative). The investigator and any designees are responsible for detecting, documenting, and reporting events that meet the definition of an AE or SAE as well as other reportable safety events. Investigators remain responsible for following up AEs, SAEs, and other reportable safety events for outcome. The investigator, who is a qualified physician, will assess events that meet the definition of an AE or SAE as well as other reportable safety events with respect to seriousness, intensity/toxicity and causality.

The following list of AEs (Section 10.1) and the characteristics of an observed AE will determine whether the event requires expedited reporting to Overall PI and DSMC via the OnCore **in addition** to routine reporting.

Time Period and Frequency for Collecting AE, SAE, and Other Reportable Safety Event Information

All AEs, SAEs, and other reportable safety events that occur after the consent form is signed but before intervention allocation/randomization must be reported by the investigator if the participant is receiving placebo run-in or other run-in treatment, if the event cause the participant to be excluded from the study, or is the result of a protocol-specified intervention, including but not limited to washout or discontinuation of usual therapy, diet, or a procedure.

- All AEs from the time of intervention allocation/randomization through 30 days following cessation of study intervention must be reported by the investigator.
- All AEs meeting serious criteria, from the time of intervention allocation/randomization through 90 days following cessation of study intervention or 30 days following cessation of study intervention if the participant initiates new anticancer therapy, whichever is earlier, must be reported by the investigator.
- All pregnancies and exposure during breastfeeding, from the time of intervention allocation/randomization through 120 days following cessation of study intervention, or 30 days following cessation of study intervention if the participant initiates new anticancer therapy must be reported by the investigator.
- Additionally, any SAE brought to the attention of an investigator at any time outside of the time period specified above must be reported immediately to Merck if the event is considered drug-related.

Investigators are not obligated to actively seek AEs or SAEs or other reportable safety events in former study participants. However, if the investigator learns of any SAE, including a death, at any time after a participant has been discharged from the study, and he/she considers the event to be reasonably related to the study intervention or study participation, the investigator must promptly notify Merck.

All initial and follow-up AEs, SAEs, and other reportable safety events will be recorded and reported to Merck within the time frames as indicated in the Table below.

Table 6. Reportable safety events.

Type of Event	Reporting Time Period: Consent to Randomization/Allocation	Reporting Time Period: Randomization/Allocation through Protocol-specified Follow-up Period	Reporting Time Period: After the Protocol-specified Follow-up Period	Time Frame to Report Event and Follow-up Information to Merck:
Serious Adverse Event (SAE) including Cancer and Overdose	Report if: - due to protocol-specified intervention - causes exclusion - participant is receiving placebo run-in or other run-in treatment	Report all	Report if: - drug/vaccine related. (Follow ongoing to outcome)	Within 2 business days but no longer than 3 calendar days of learning of event
Pregnancy/Lactation Exposure	Report if: - due to intervention - causes exclusion	Report all	Previously reported – Follow to completion/termination; report outcome	Within 2 business days but no longer than 3 calendar days of learning of event
Event of Clinical Interest (require regulatory reporting)	Report if: - due to intervention - causes exclusion	Report - potential drug-induced liver injury (DILI) - require regulatory reporting	Not required	Within 2 business days but no longer than 3 calendar days of learning of event

Method of Detecting AEs, SAEs, and Other Reportable Safety Events

Care will be taken not to introduce bias when detecting AEs and/or SAEs and other reportable safety events. Open-ended and nonleading verbal questioning of the participant is the preferred method to inquire about AE occurrence.

Follow-up of AE, SAE, and Other Reportable Safety Event Information

After the initial AE/SAE report, the investigator is required to proactively follow each participant at subsequent visits/contacts. All AEs, SAEs, and other reportable safety events including pregnancy and exposure during breastfeeding, events of clinical interest (ECIs), cancer, and

overdose will be followed until resolution, stabilization, until the event is otherwise explained, or the participant is lost to follow-up. In addition, the investigator will make every attempt to follow all nonserious AEs that occur in randomized participants for outcome.

Sponsor Responsibility for Reporting Adverse Events

All Adverse Events will be reported to regulatory authorities, IRB/IECs and investigators in accordance with all applicable country specific regulatory requirements, global laws and regulations.

Pregnancy and Exposure During Breastfeeding

Although pregnancy and infant exposure during breastfeeding are not considered AEs, any pregnancy or infant exposure during breastfeeding in a participant (spontaneously reported to the investigator or their designee) that occurs during the study are reportable to Merck.

All reported pregnancies must be followed to the completion/termination of the pregnancy. Pregnancy outcomes of spontaneous abortion, missed abortion, benign hydatidiform mole, blighted ovum, fetal death, intrauterine death, miscarriage, and stillbirth must be reported as serious events (Important Medical Events). If the pregnancy continues to term, the outcome (health of infant) must also be reported.

Events of Clinical Interest (ECIs)

Selected nonserious and SAEs are also known as ECIs and must be reported to Merck.

Events of clinical interest for this study include:

